## **6 ANALYSIS VARIABLES**

The value at presurgery will be used as the baseline unless otherwise specified for each endpoint. In case of missing value at presurgery, the last measurement before surgery will be used as the baseline.

The eGFR(SCr) will be calculated using the GFR estimation equation (2009 CKD-EPI creatinine equation) [KDIGO, 2013]. The subject's age at visit 1 should be used for calculation in this study.

Gender	Serum Creatinine	Equation for Estimating GFR
Female	$\leq 0.7 \text{ mg/dl} (\leq 62 \text{ } \mu\text{mol/l})$	$144 \times (\text{SCr}/0.7)^{-0.329} \times 0.993^{\text{Age}} [\times 1.159 \text{ if black}]$
Female	$> 0.7 \text{ mg/dl} (> 62 \text{ } \mu\text{mol/l})$	$144 \times (\text{SCr}/0.7)^{-1.209} \times 0.993^{\text{Age}} [\times 1.159 \text{ if black}]$
Male	$\leq 0.9 \text{ mg/dl} (\leq 80 \text{ } \mu\text{mol/l})$	$141 \times (\text{SCr}/0.9)^{-0.411} \times 0.993^{\text{Age}} [\times 1.159 \text{ if black}]$
Male	$> 0.9 \text{ mg/dl} (> 80 \text{ } \mu\text{mol/l})$	$141 \times (\text{SCr}/0.9)^{-1.209} \times 0.993^{\text{Age}} [\times 1.159 \text{ if black}]$

GFR: glomerular filtration rate; SCr: serum creatinine

Reference: KDIGO 2012 Clinical Practice Guideline for the Evaluation and Management of Chronic Kidney Disease. Official Journal of the International Society of Nephrology: Kidney International Supplements. 2013;3(1):1-150.

The eGFR(serum cystatin C [SCysC]) will be calculated using the GFR estimation equation (2012 CKD-EPI cystatin C equation) [KDIGO, 2013]. The subject's age at visit 1 should be used for calculation in this study.

Gender	Serum Creatinine	Equation for Estimating GFR
Female	$\leq 0.8 \text{ mg/dl}$	$133 \times (\text{SCysC}/0.8)^{-0.499} \times 0.996^{\text{Age}} \times 0.932$
Female	$> 0.8 \text{ mg/dl}$	$133 \times (\text{SCysC}/0.8)^{-1.328} \times 0.996^{\text{Age}} \times 0.932$
Male	$\leq 0.8 \text{ mg/dl}$	$133 \times (\text{SCysC}/0.8)^{-0.499} \times 0.996^{\text{Age}}$
Male	$> 0.8 \text{ mg/dl}$	$133 \times (\text{SCysC}/0.8)^{-1.328} \times 0.996^{\text{Age}}$

GFR: glomerular filtration rate; SCysC: serum cystatin C

Reference: KDIGO 2012 Clinical Practice Guideline for the Evaluation and Management of Chronic Kidney Disease. Official Journal of the International Society of Nephrology: Kidney International Supplements. 2013;3(1):1-150.

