## 2.3 Endpoints

The current study will focus on assessing the emergence of AKI. AKI can be defined in various different ways, but in this study AKI KDIGO stage determination criteria are utilized [KDIGO, 2012].

AKI is defined as any of the following:

- Increase in SCr by  $\geq 0.3$  mg/dl ( $\geq 26.5$   $\mu$ mol/L) within 48 hours
- Increase in SCr to  $\geq 1.5$  times baseline, which is known or presumed to have occurred within the prior 7 days or
- UO  $< 0.5$  ml/kg per hour for 6 hours or more

The eGFR(SCr) will be calculated using the GFR estimation equation (2009 CKD-EPI creatinine equation) [KDIGO, 2013]. The subject's age at visit 1 should be used for calculation in this study.

| Gender | Serum Creatinine                          | Equation for Estimating GFR  |
|--------|---|--|
| Female | $\leq 0.7$ mg/dl ( $\leq 62$ $\mu$ mol/l) | $144 \times (\text{SCr}/0.7)^{-0.329} \times 0.993^{\text{Age}} [\times 1.159 \text{ if black}]$ |
| Female | $> 0.7$ mg/dl ( $> 62$ $\mu$ mol/l)       | $144 \times (\text{SCr}/0.7)^{-1.209} \times 0.993^{\text{Age}} [\times 1.159 \text{ if black}]$ |
| Male   | $\leq 0.9$ mg/dl ( $\leq 80$ $\mu$ mol/l) | $141 \times (\text{SCr}/0.9)^{-0.411} \times 0.993^{\text{Age}} [\times 1.159 \text{ if black}]$ |
| Male   | $> 0.9$ mg/dl ( $> 80$ $\mu$ mol/l)       | $141 \times (\text{SCr}/0.9)^{-1.209} \times 0.993^{\text{Age}} [\times 1.159 \text{ if black}]$ |

GFR: glomerular filtration rate

Reference: KDIGO 2012 Clinical Practice Guideline for the Evaluation and Management of Chronic Kidney Disease. Official Journal of the International Society of Nephrology: Kidney International Supplements. 2013;3(1):1-150.

The eGFR(SCysC) will be calculated using the GFR estimation equation (2012 CKD-EPI cystatin C equation) [KDIGO, 2013]. The subject's age at visit 1 should be used for calculation in this study.

| Gender | Serum Creatinine  | Equation for Estimating GFR  |
|---------------|--------------------------|---|
| Female        | $\leq 0.8 \text{ mg/dl}$ | $133 \times (\text{SCysC}/0.8)^{-0.499} \times 0.996^{\text{Age}} \times 0.932$ |
| Female        | $> 0.8 \text{ mg/dl}$    | $133 \times (\text{SCysC}/0.8)^{-1.328} \times 0.996^{\text{Age}} \times 0.932$ |
| Male          | $\leq 0.8 \text{ mg/dl}$ | $133 \times (\text{SCysC}/0.8)^{-0.499} \times 0.996^{\text{Age}}$              |

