### **6.1.3 Exploratory Efficacy Endpoints**

For the exploratory efficacy endpoints of proportion of events, subjects whose status of events are unknown due to, e.g., missing data will not be counted as the events, unless specifically stated otherwise.

1. All-cause mortality at day 30 (Visit 9)
2. All-cause mortality at day 90 (Visit 10)
3. Number of subjects needing RRT at day 30 (Visit 9)
4. Number of subjects needing RRT at day 90 (Visit 10)
5. Number of subjects with  $\geq 25\%$  sustained reduction in eGFR based on SCr at day 30 (Visit 9)
6. Number of subjects with  $\geq 25\%$  sustained reduction in eGFR based on SCr at day 90 (Visit 10)
7. Proportion of subjects with MAKE defined as all-cause mortality, RRT and/or  $\geq 25\%$  sustained reduction in eGFR based on cystatin-C within 30 days after day of surgery (MAKE30 with eGFR based on cystatin-C).
  - If the subject meets at least one of the following conditions by day 30 (Visit 9), then the subject will be treated as with MAKE30 with eGFR based on cystatin-C.
    - All-cause mortality;
    - Initiation of RRT; and/or,
    - eGFR based on cystatin-C at day 30 (Visit 9) equal to or less than 75% of the baseline value.
8. Proportion of subjects with MAKE defined as all-cause mortality, RRT and/or  $\geq 25\%$  sustained reduction in eGFR based on cystatin-C within 90 days after day of surgery (MAKE90 with eGFR based on cystatin-C).
  - If the subject meets at least one of the following conditions by day 90 (Visit 10), then the subject will be treated as with MAKE90 with eGFR based on cystatin-C.
    - All-cause mortality;
    - Initiation of RRT; and/or,
    - eGFR based on cystatin-C at day 90 (Visit 10) equal to or less than 75% of the baseline value.
9. Number of subjects with  $\geq 25\%$  sustained reduction in eGFR based on cystatin-C at day 30 (Visit 9)
10. Number of subjects with  $\geq 25\%$  sustained reduction in eGFR based on cystatin-C at day 90 (Visit 10)
11. Number of hospital days during initial hospitalization
  - The number of hospital days per subject during initial hospitalization will be calculated as: Date of discharge – Date of admission + 1 (for the initial hospitalization including ICU).
    - Initial hospitalization is a hospitalization which includes the day of surgery
    - If the date of admission of a hospitalization record is the same as the date of discharge of the previous record, for example because two records are created to

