**Table 9 Baseline values of efficacy variables**

Item	Classification
Serum Creatinine (mg/dL)	Measurement value
Cystatin-C (mg/L)	Measurement value
eGFR based on Serum Creatinine (mL/min/1.73 m  )	Measurement value 1: < 45 2: >= 45 1: < 60 2: >= 60
eGFR based on Cystatin-C (mL/min/1.73 m  )	Measurement value 1: < 45 2: >= 45 1: < 60 2: >= 60

eGFR: estimated glomerular filtration rate

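### The cystatin C eGFR table carries the wrong branch heading and a mg/dl cut-off that conflicts with mg/L data; programmed literally, it would misstate the exploratory cystatin-eGFR items

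*SAP*

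**What the plan says.** SAP section 6 gives two equation tables, one for creatinine eGFR and one for cystatin C eGFR. For the latter the value "will be calculated using the GFR estimation equation (2012 CKD-EPI cystatin C equation"). The equation has two branches that meet at 0.8, with exponent −0.499 at or below the cut-off and −1.328 above it. The concentration is divided by 0.8 in both branches. The column that defines the branch is headed "Serum Creatinine", as in the creatinine table above it, and all four rows give the cut-off in mg/dl. The formula itself uses SCysC, which the SAP footnote defines as serum cystatin C.

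Protocol section 2.3 repeats the statement ("The eGFR(SCysC) will be calculated using the GFR estimation equation (2012 CKD-EPI cystatin C equation") and the table, with the same heading and unit.

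SAP Table 9 lists the baseline variable as "Cystatin-C (mg/L"), and plans categories of cystatin eGFR split at 45 and at 60. Neither document states a conversion between mg/L and mg/dl.

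The derived eGFR feeds endpoints in SAP 6.1.3 such as "eGFR based on cystatin-C at day 30 (Visit 9) equal to or less than 75% of the baseline value".

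**The concern.** There are two separate faults: a unit that disagrees with the data by a factor of ten, and a heading that names the wrong analyte as the branch variable. A unit slip often cancels in endpoints defined as a ratio to baseline. Here it need not, because the unit also decides which exponent applies, and the exponent sets how large a rise in cystatin C counts as a 25% or 50% fall in eGFR.

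The items that depend on this equation are:

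- MAKE30 and MAKE90 with cystatin eGFR;
- a reduction of at least 25% in cystatin eGFR at days 30 and 90;
- AKI defined as a fall of at least 50% in cystatin eGFR within 72 hours and within 7 days;
- change from baseline in cystatin eGFR;
- the baseline cystatin-eGFR summary and categories in Table 9.

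Under SAP 7.4.4 the proportions are tested with CMH and reported as risk ratios, and the change from baseline is compared by t-test. Two programmers working from the printed table could therefore report different event counts.

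**Working it through.** The plan contains no worked eGFR, so there is no figure to reproduce. The check evaluates the printed formula under each reading that the text allows.

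**Inputs.** From SAP 6: eGFR = 133 × (c/0.8)^k × 0.996^age, times 0.932 for women, with k = −0.499 or −1.328. From SAP Table 9: data in mg/L. Assumed for illustration: a man aged 70, and cystatin C between 0.6 and 3.0 mg/L, because the documents give no range.

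**Common factor.** 133 × 0.996^70 = 100.5 for men; 100.5 × 0.932 = about 93.6 for women.

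**Three readings of the unit**

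- A: mg/L value entered as it is, branch on cystatin C at 0.8 mg/L.
- B: value divided by 10 to give mg/dl, as the table's unit implies.
- C: branch tested in mg/dl, but the mg/L number used in the ratio.

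| Cystatin C (mg/L) | A | B | C |
|---|---|---|---|
| 0.8 | 100.5 | 317.0 | 100.5 |
| 1.0 | 74.7 | 283.6 | 89.9 |
| 1.2 | 58.6 | 258.9 | 82.1 |
| 1.5 | 43.6 | 231.6 | 73.4 |
| 2.0 | 29.8 | 200.6 | 63.6 |
| 3.0 | 17.4 | 163.9 | 51.9 |

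For example, at 1.2 mg/L, A is 100.5 × 1.5^−1.328 = 58.6 and B is 100.5 × 0.15^−0.499 = 258.9.

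**Table 9 categories under B.** At 8 mg/L (0.8 mg/dl) the eGFR is still 100.5 in men and 93.6 in women. For a man to fall below 60, c must exceed 0.8 × (100.5/60)^(1/1.328) = 1.18 mg/dl, or 11.8 mg/L. Below 45 needs about 14.7 mg/L. Both low categories would be empty over the assumed range.

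**Rise needed for an event.** On one branch, a fall of r needs a rise of (1 − r)^(−1/|k|):

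- 25% fall: 0.75^(−1/1.328) = 1.24-fold (A); 0.75^(−1/0.499) = 1.78-fold (B).
- 50% fall: 0.5^(−1/1.328) = 1.69-fold (A); 0.5^(−1/0.499) = 4.01-fold (B).

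The A figures hold for a baseline of at least 0.8 mg/L. From 0.6 mg/L the rise crosses the branch, and a 25% fall then needs about 1.49-fold. C uses the same exponent as B over this range, so it needs the same rises as B.

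Example: cystatin C rising from 1.0 to 1.5 mg/L is a 41.6% fall under A (an event at the 25% threshold) and an 18.3% fall under B (no event).

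**Reading of the heading (D): creatinine chooses the branch, cystatin C in mg/L.** At 1.5 mg/L the eGFR is 73.4 if creatinine is at or below 0.8 and 43.6 if it is above. If creatinine crosses 0.8 upward while cystatin C stays at 1.5 mg/L, the apparent fall is 1 − (1.5/0.8)^−(1.328 − 0.499) = 1 − 1.875^−0.829 = 40.6%. The false fall reaches 25% once cystatin C exceeds 0.8 × 0.75^(−1/0.829) = 1.13 mg/L.

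**The case against.** The strongest reply is that nobody is told to divide by ten. The equation is named and referenced, the formula is written in SCysC, and SCysC is defined. A programmer who enters mg/L values and branches on SCysC (reading A) gets sensible results. Table 9's splits at 45 and 60 show the intended scale, and a typical eGFR near 259 would be noticed. The central laboratory panel (protocol 5.4.2, Table 7) also lists a cystatin-based eGFR.

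Much of this stands: the harm is conditional. But reading A means overriding both the printed unit and the printed heading. Readings C and D do not announce themselves, since their values (82.1 at 1.2 mg/L under C, for instance) look ordinary while event status is wrong. Neither document names the laboratory's eGFR as the analysis source, and the SAP says the value is calculated from this table.

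A reader might also infer that every cystatin C endpoint is compromised. The documents do not support that. The serum rises of at least 10% and at least 25%, the change in serum cystatin C, and the cystatin C areas under the curve use measured concentrations and never call the equation.

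**Conclusion.** The table is wrong as written in both documents, and the same two faults in each make it unlikely that they come from reading the PDF. Followed literally, it changes values and event status. Conversion to mg/dl would miss events, because the required rises go from 1.24- to 1.78-fold and from 1.69- to 4.0-fold (baseline at least 0.8 mg/L). Branching on creatinine could create them, with an apparent 40.6% fall at an unchanged 1.5 mg/L.

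The reach is limited. Every affected endpoint is exploratory, and Table 9 is a baseline description. A reader who sees MAKE30 and MAKE90 in the list might think the secondary endpoints are touched. They are not: SAP 6.1.2 defines them on creatinine eGFR. The primary endpoint, the stratification factor and the sample size do not use cystatin C either.

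The conclusion rests on two assumptions. One is the illustrative range of 0.6 to 3.0 mg/L. The other is that mg/L is the intended unit, which is inferred from Table 9's unit and from its categories at 45 and 60, not from the cited guideline. The point should be corrected, but it does not threaten the trial's main conclusions.

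**What to change.** In SAP section 6 and protocol section 2.3, head the branch column of the cystatin C table 'Serum cystatin C', give the cut-off as 0.8 mg/L in all four rows, and add one sentence stating that SCysC is entered in mg/L. It would also help to state in the SAP whether the analysis uses this derived eGFR or the central laboratory's value.

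The cost is one heading and four unit cells in each document, plus the added sentence. No analysis, endpoint or sample size changes. Protocol 12.1.3 requires changes after approval to be documented as an amendment, so the protocol correction needs that step. The SAP correction belongs in its revision history.

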## 6.1 Efficacy Endpoints

### 6.1.1 Primary Efficacy Endpoint

Proportion of subjects developing AKI (any stage) based on SCr criteria from the KDIGO guideline within 72 hours after T0 (AKI-SCr72h).

[SCr evaluation visit: baseline, Visit 3, 4 and 5 (24, 48, 72 hours after T0)]

- If the subject meets at least one of the following conditions, then the subject will be treated as developing AKI-SCr72h.
  - Increasing in SCr  $\geq 0.3 \text{ mg/dL}$  within any 48 hours until Visit 5; and/or,
  - Increasing in SCr  $\geq 1.5$  times baseline until Visit 5.

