### 2.3.1 Primary Endpoints

Proportion of subjects developing AKI (any stage) based on SCr criteria from the KDIGO guideline (i.e., increase in SCr  $\geq 0.3 \text{ mg/dL}$  [ $\geq 26.5 \mu\text{mol/L}$ ] within any 48 hours, or increase in SCr to  $\geq 1.5$  times baseline) within 72 hours after T0 (AKI-SCr72h).

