**Table 3 Definitions of Stages**

Stage	AKI-SCr	AKI-UO
1	$\geq 1.5$ to $< 2$ times baseline, or Increasing $\geq 0.3$ mg/dL within any 48 hours	(Not used for this study)
2	$\geq 2$ to $< 3$ times baseline	$< 0.5$ mL/kg per hour for over 12 hours
3	$\geq 3$ times baseline, Increase in serum creatinine to $\geq 4.0$ mg/dL, or Initiation of RRT	$< 0.3$ mL/kg per hour for over 24 hours, or Anuria for over 12 hours

AKI-SCr: acute kidney injury based on serum creatinine KDIGO criteria; AKI-UO: acute kidney injury based on urinary output; RRT: renal replacement therapy

KDIGO Clinical Practice Guideline for Acute Kidney Injury. Official Journal of the International Society of Nephrology: Kidney International Supplements. 2012;2(1):1-138.

16. Alternative derivations of proportion of subjects developing AKI using different definitions [Table 3] within 7 days after T0.
17. Proportion of subjects developing AKI (any stage) based on SCr criteria from the KDIGO guideline within 5 days after T0 (i.e., until Visit 6) (AKI-SCr5d).  
[SCr evaluation visit: baseline, Visit 3, 4, 5 and 6 (24 hours, 48 hours, 72 hours after T0, and Day 5). If the hospital discharge is earlier than Day 5, then the visits prior to DoD and Visit 8 (DoD) will be used.]
  - If the subject meets at least one of the following conditions, then the subject will be treated as developing AKI-SCr5d.
    - Increasing in SCr  $\geq 0.3$  mg/dL within any 48 hours until Visit 6; and/or,
    - Increasing in SCr  $\geq 1.5$  times baseline until Visit 6.
18. Proportion of subjects developing AKI based on all criteria from the KDIGO guideline within 5 days after T0 (AKI-KDIGO5d).  
[SCr evaluation visit: baseline, Visit 3, 4, 5 and 6 (24 hours, 48 hours, 72 hours after T0, and Day 5). If the hospital discharge is earlier than Day 5, then the visits prior to DoD and Visit 8 (DoD) will be used.]  
[UO evaluation visit: Visit 3, 4, 5 and 6 (0-12 hours, 12-24 hours, 0-24 hours, ..., and 72-84 hours, 84-96 hours and 72-96 hours after T0). If the hospital discharge is earlier than Day 5, then the visits prior to DoD and Visit 8 (DoD) will be used.]
  - If the subject meets at least one of the following conditions, then the subject will be treated as developing AKI-KDIGO5d.
    - Increasing in SCr  $\geq 0.3$  mg/dL within any 48 hours until Visit 6;
    - Increasing in SCr  $\geq 1.5$  times baseline until Visit 6; and/or,

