    - Urine volume  $< 0.5$  ml/kg per hour for any one of 12 consecutive hours until Visit 6 (i.e., 0-12 hours after T0, 12-24 hours after T0, ..., or 84-96 hours after T0).
19. Severity of AKI within 72 hours after T0
  - Severity of AKI based on AKI-SCr stages (Stage 1, 2, 3 or no AKI. No AKI means subject not developing AKI-SCr72h.)

- Severity of AKI based on AKI-UO stages (Stage 2, 3, or no AKI. No AKI means subject not developing AKI-UO)
- Severity of AKI based on most severe of AKI-SCr or AKI-UO stages (Stage 1, 2, 3 or no AKI)

20. Severity of AKI (based on AKI stage using SCr and/or UO) within 7 days after T0

21. Duration of AKI based on AKI stage using SCr

- Duration of AKI-SCr72h: time from moment of first meeting criteria for AKI-SCr72h until moment of first not meeting the criteria for AKI-SCr72h, death or hospital discharge. If the duration of AKI-SCr72h exceeds day 7 the time of ending of AKI will be assessed retrospectively on day 30 (visit 9) based on local SCr laboratory results. The date and value when respective criteria of AKI-SCr72h were resolved is recorded in the eCRF as an unscheduled event with check of “First NOT meeting the criteria for AKI-SCr72h/7d (SCr  $\geq$ 1.5 times baseline) before hospital discharge, if the duration of AKI-SCr72h/7d exceeds Visit 8 (Day 7).”.
- The duration will be calculated as follows;  
(Date of first not meeting the criteria, death or hospital discharge – Date of first meeting the criteria) in days.  
For subjects who don't occur AKI-SCr72h, the duration of AKI will be treated as 0.
- Duration of AKI-SCr7d (definition as above)

22. Time to AKI-SCr72h (i.e., the time from T0 to the time when criteria for AKI-SCr72h are met). The time to AKI-SCr72h will be calculated as: (Date of first meeting the criteria – Date of T0 + 1) in days.

23. Time to AKI-SCr7d (definition as above)

24. Proportion of subjects with AKI as defined by a 50% or higher reduction in eGFR based on the cystatin-C equation within 72 hours after T0.

- If the subject meet the following condition, then the subject will be treated as with AKI for this endpoint.
  - At least one of eGFR based on cystatin-C equation within 72 hours after T0  $\leq$  50% of the baseline value.

25. Proportion of subjects with AKI as defined by a 50% or higher reduction in eGFR based on the cystatin-C equation within 7 days after T0.

- If the subject meet the following condition, then the subject will be treated as with AKI for this endpoint.

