#### 7.4.4 Analysis of Exploratory Endpoints

[Analysis population: FAS, Analysis group: Randomization Arm]

The following analysis will be conducted for endpoint group 1.

- The proportion of subjects who meet the criteria will be analyzed using the CMH test with strata to control for baseline eGFR ( $< 45$ ,  $\geq 45$ ).
- The MH estimate of the adjusted common risk ratio and 2-sided 90% confidence interval will be calculated.
- If the proportion of subjects with baseline eGFR based on Serum Creatinine  $< 45$  mL/min per 1.73 m^2 for FAS is less than 10%, the above stratified analyses of CMH test and MH estimate of adjusted common risk ratio will be replaced with unstratified analyses of chi-square test and unadjusted risk ratio.

Group 1:

- All-cause mortality at day 30 (Visit 9)
- All-cause mortality at day 90 (Visit 10)
- Number of subjects needing RRT at day 30 (Visit 9)
- Number of subjects needing RRT at day 90 (Visit 10)
- Number of subjects with  $\geq 25\%$  sustained reduction in eGFR based on SCr at day 30 (Visit 9)
- Number of subjects with  $\geq 25\%$  sustained reduction in eGFR based on SCr at day 90 (Visit 10)
- MAKE30 with eGFR based on cystatin-C
- MAKE90 with eGFR based on cystatin-C
- Number of subjects with  $\geq 25\%$  sustained reduction in eGFR based on cystatin-C at day 30 (Visit 9)
- Number of subjects with  $\geq 25\%$  sustained reduction in eGFR based on cystatin-C at day 90 (Visit 10)
- Alternative derivations of proportion of subjects developing AKI using different definitions [[Table 3](#)] within 72 hours after T0. The stages will be used for subject developing AKI-SCr72h.
  - All stages AKI-UO (AKI-UO stage 2 or stage 3)
  - AKI-UO stage 3
  - AKI-SCr stage 2 or 3
  - AKI-SCr stage 2 or 3 and/or AKI-UO stage 3
  - AKI based on Cystatin-C, defined as an increase of  $\geq 10\%$  of baseline serum cystatin-C [[KDIGO, 2012](#)]

- Alternative derivations of proportion of subjects developing AKI using different definitions within 7 days after T0.
- AKI-SCr5d
- AKI-KDIGO5d
- Proportion of subjects with AKI as defined by a 50% or higher reduction in eGFR based on the Cystatin-C equation within 72 hours after T0.
- Proportion of subjects with AKI as defined by a 50% or higher reduction in eGFR based on the Cystatin-C equation within 7 days after T0.
- Proportion of subjects that have a reduction of NC AKIRisk score 24 hours after T0 (visit 3) to or below  $0.3 \text{ (ng/ml)}^2/1000$

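### The AKI-SCr event rules leave out initiation of RRT, although both staging tables make it stage 3, so a subject dialysed early can be scored as having no AKI

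*SAP*

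**What the plan says.** Protocol 2.3.1 names the primary endpoint as "Proportion of subjects developing AKI (any stage) based on SCr criteria from the KDIGO guideline". It then spells this out as two creatinine changes, 0.3 mg/dL within any 48 hours or 1.5 times baseline, within 72 hours of T0. SAP 6.1.1 implements the same two conditions, using creatinine at baseline and at Visits 3, 4 and 5: "If the subject meets at least one of the following conditions, then the subject will be treated as developing AKI-SCr72h". The first ends "within any 48 hours until Visit 5; and/or" and the second "times baseline until Visit 5". RRT is in neither.

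Staging is defined elsewhere. In SAP Table 3 the stage 3 entry for AKI-SCr ends "or Initiation of RRT". Protocol Table 3 also lists the start of RRT under stage 3, in the serum creatinine column.

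Two SAP statements tie staging back to the event rule:

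- SAP 6.1.3, item 19 (creatinine-based severity within 72 hours): "No AKI means subject not developing AKI-SCr72h".
- SAP 7.4.4, Group 1 (alternative AKI proportions within 72 hours): "The stages will be used for subject developing AKI-SCr72h".

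SAP 6.1.3, item 21, sets AKI duration to 0 for subjects without AKI-SCr72h. SAP 6.1.2 counts RRT initiation as an event in its own right only for MAKE30 and MAKE90.

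**The concern.** Dialysis lowers serum creatinine. A subject who starts RRT between two daily samples may therefore never show a qualifying rise at a scheduled visit. Under the staging tables that subject has stage 3 AKI on creatinine criteria. Under the event rule the subject is a non-event, so the most severe renal course is recorded as the most favourable one.

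The error would carry into several analyses:

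- the primary endpoint, AKI-SCr5d and AKI-SCr7d;
- AKI-KDIGO72h, 5d and 7d, unless low urine output captures the subject;
- the Wilcoxon tests on creatinine-based severity and on AKI duration;
- the proportion with AKI-SCr stage 2 or 3, which would leave the subject out;
- time to AKI-SCr72h, where the subject would be censored at Visit 5.

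The AKI-by-MAKE contingency tables in SAP 7.4.2 could then show RRT without AKI-SCr, purely because of the derivation.

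**Working it through.** **1. Score one illustrative subject.** Take baseline creatinine 1.2 mg/dL, RRT started early, then 1.3, 1.4 and 1.2 mg/dL at 24, 48 and 72 hours.

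- Largest rise: 1.4 − 1.2 = 0.2 mg/dL, below 0.3.
- Largest ratio: 1.4 / 1.2 = 1.17, below 1.5.

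Both conditions fail, so AKI-SCr72h is no, creatinine-based severity is no AKI and duration is 0. By SAP Table 3 the same subject is stage 3, and by SAP 6.1.2 the same subject is a MAKE30 event.

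**2. Look for a rule that rescues the case.** SAP Table 10 refers missing-data handling for the primary analysis to Section 6.1, and 6.1.1 says nothing about creatinine after RRT starts. The multiple imputation (Sensitivity 3) and the count-as-event rule (Sensitivity 4) act only on missing creatinine. This subject has every value, so neither applies.

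**3. Check whether the other stage 3 criterion, SCr of 4.0 mg/dL or more, is also a gap.** Exclusion criterion 10 sets the lowest eligible eGFR at 30, and the minimum age is 35. Inverting the SAP's creatinine equation for the case with the highest baseline (male, age 35, with the race coefficient):

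SCr = 0.9 × (141 × 0.993^35 × 1.159 / 30)^(1/1.209) = 2.98 mg/dL.

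Reaching 4.0 needs a rise of at least 4.0 − 2.98 = 1.02 mg/dL. Baseline to 24 hours and 24 to 72 hours are each within 48 hours, so one of them must contain at least 1.02 / 2 = 0.51 mg/dL. The 0.3 mg/dL condition is then already met. If 4.0 is reached at 24 or 48 hours the same argument applies to the shorter span. The criterion adds nobody when baseline eGFR is at least 30 and all values are present on schedule.

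**4. Sensitivity of the primary analysis.** The plan's design figure first: 110 per arm less 10% dropout is 99 per arm, with rates 0.60 and 0.60 × 0.7 = 0.42, one-sided 0.05, pooled-variance test:

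z = (0.18 × √99 − 1.645 × √(2 × 0.51 × 0.49)) / √(0.60 × 0.40 + 0.42 × 0.58) = 0.90, so power is 81.7% against the stated 80%.

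Now treat 60% and 42% as the rates with RRT counted, and let some of these events be missed. The amounts missed are assumptions chosen to show sensitivity. They are not estimates.

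| Percentage points missed | Power, missed in both arms (RR stays 0.7) | Power, missed in placebo only | Observed RR, missed in ASP1128 only |
|---|---|---|---|
| 1 | 80.5% | 77.6% | 0.683 |
| 2 | 79.3% | 73.1% | 0.667 |
| 3 | 78.1% | 68.1% | 0.650 |
| 5 | 75.5% | 57.4% | 0.617 |

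In the both-arms column the points refer to placebo, and ASP1128 loses 0.7 times as many. The last column is, for example, (0.42 − 0.01) / 0.60 = 0.683. One percentage point is about one subject of 99. Balanced loss costs little. Loss in one arm moves the result, in either direction.

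**The case against.** The strongest defence is that the plan diagnoses first and stages second. Protocol 2.3 defines AKI by the two creatinine changes or urine output, without RRT, and only then grades severity. On that reading RRT raises the stage of a subject who already has AKI. Keeping a clinician's decision out of an endpoint labelled as creatinine-based is defensible, and Protocol 1.1 notes that the timing of RRT initiation is unsettled. RRT is also not lost from the trial: it counts in MAKE30 and MAKE90, is tested separately at days 30 and 90, and an oliguric subject may enter AKI-KDIGO72h through urine output.

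This shows that the choice can be argued. It does not remove the conflict between an any-stage label, a creatinine stage 3 that includes RRT, and a rule that cannot reach it. None of the other endpoints corrects the primary one.

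Four stronger readings should not be drawn:

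- That the SAP departs from the protocol. Protocol 2.3.1 contains the same two conditions, so the gap is in both documents.
- That leaving out SCr of 4.0 mg/dL or more is an equal gap. Step 3 shows it has no effect under the stated conditions. It could matter only with intermediate values missing, or for a subject whose central-laboratory eGFR below 30 arrives after randomization.
- That the 1.6% to 5.8% dialysis rate in Protocol 1.1 gives the number affected. It is a general cardiac-surgery figure with no 72-hour limit, and it counts patients whose AKI led to dialysis, not RRT without a creatinine rise.
- That the staging sentence in SAP 7.4.4 governs the severity test. It sits under the alternative AKI proportions. The severity consequence rests on SAP 6.1.3, item 19, and is explicit there only for creatinine-based severity within 72 hours.

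**Conclusion.** The point holds for RRT. Followed as written, the plan scores a subject who starts RRT before a qualifying scheduled creatinine as a non-event in AKI-SCr72h, as no AKI in creatinine-based severity and as duration 0. The same subject is left out of the AKI-SCr stage 2 or 3 proportion and is counted in MAKE30 and MAKE90.

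The size cannot be derived from the documents, which give no rate of RRT within 72 hours without a qualifying rise. It is likely to be a few subjects at most, because a 0.3 mg/dL rise is a low threshold sampled daily and many dialysed subjects will meet it first. A reader might infer that an arm with more early RRT would generally look better. That follows only for RRT started before any qualifying creatinine, so the possible bias is narrow. It still deserves correction, because each such subject moves from the worst category to the best and the planned missing-data analyses would not show it.

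**What to change.** Before unblinding:

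1. Count initiation of RRT within the relevant window as an event for AKI-SCr72h, 5d and 7d and for AKI-KDIGO72h, 5d and 7d (SAP 6.1.1, 6.1.2 and 6.1.3, items 17 and 18).
2. Assign stage 3 from SAP Table 3 whether or not the creatinine-rise conditions are met, and amend the two statements in SAP 6.1.3, item 19, and 7.4.4 that restrict staging to subjects with AKI-SCr72h.
3. Align Protocol 2.3.1 and 2.3.2.

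There is no need to add SCr of 4.0 mg/dL or more to the event rule.

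The cost is a protocol clarification as well as the SAP edit and derivation. The endpoint also gains a component decided by clinicians. Sample size and significance level stay as they are. RRT data are already assessed at the visits (footnote 13 of the schedule for randomized subjects) and used for MAKE. It should be confirmed that the start is recorded precisely enough to apply a 72-hour window, since the documents do not say so. If the sponsor prefers to keep RRT out, the SAP should justify that and report by arm how many subjects started RRT in each window without meeting the creatinine conditions.
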